1 PROTOCOL SUMMARY

1.1 SYNOPSIS

Protocol Title: *Intervention to Educate and Improve Underserved Populations' Participation in Clinical Trials and the Uptake and Completion of the HPV Vaccine Series*

Objectives:

- **Primary Objective:**
 - 1) *Educate parents (and young adults) via CHEs about the HPV vaccine, in order improve knowledge and intentions to increase uptake of the vaccine for individuals aged 9-26.*
 - 2) *We will collect socio-demographic data to explore its association with knowledge, intentions, & vaccine uptake.*
- **Secondary Objectives:**
 - 1) *Increase completion of the HPV vaccine via PN to promote uptake of one, two, or three vaccine doses among adolescents and young adults (9-26 years old).*
 - 2) *Assess intervention delivery and patient-, clinic-, and system-level impact of the PN intervention to increase vaccine completion among adolescents and young adults.*

Endpoint:

- **Primary Endpoint:**
 - 1) *Knowledge and intentions to initiate or complete the HPV vaccine series among project participants.*
 - 2) *Association of sociodemographic variables (e.g., age, gender, ethnicity, health insurance, income, zip code) to knowledge, intentions, and uptake of the HPV vaccine among participants*
- **Secondary Endpoints:**

- 1) *Uptake of one, two, or three HPV vaccine doses among adolescents (9 to 17 years of age)*
- 2) *Uptake of one, two, or three HPV vaccine doses among young adults (18-26 years of age).*

- ***Tertiary/exploratory:***

- 1) *To assess PN impact we will record the number of participants to whom the PN scheduled to, a) receive a recommended 1st dose, 2nd dose, or 3rd dose of the HPV vaccine; b) connect to care services such as health insurance, discount or no-cost HPV vaccine programs, and c) facilitate other services such as language translation, appointment scheduling assistance, transportation services, and childcare.*
- 2) *To assess patient-level impact, we will track for each participant their (a) baseline HPV vaccine doses, and (b) the number of those they obtained in total, and quarterly (c) the number of patients who received a 1st dose, 2nd dose, or 3rd dose of the HPV vaccine.*
- 3) *To assess clinic-level impact, we will obtain clinic vaccination reports track the number of patients at each clinic who received: (a) 1st dose, 2nd dose, or 3rd dose of the HPV vaccine at baseline; and record quarterly: (b) 1st dose, 2nd dose, or 3rd dose of the vaccine broken by age for adolescents (9 to 17 years old) and young adults (18-26 years old).*

Population:

- ***Sample size***

- *Maximum number of participants that can be enrolled is 1000*
- *Minimum number of participants to be enrolled 400 (number of participants needed for analyses)*

Phase: N/A

Participating Sites: Denver Health and Hospital Authority

Description of Study

Intervention: Education and Patient Navigation

[figure not shown]
Study Duration: 36 months

Participant Duration:

Duration will vary for each participant and will be determined by vaccination status. Participants will be contacted to complete a post-education at baseline using the NCI survey. We will only administer the survey pages 1-3.

1.3 STUDY SCHEMA

Figure 1. Delivery Schema for Subjects Recruited to Participate in the CHE and PN Intervention

Note: CHE=Community Health Educator; PN=Patient Navigator; HPV=Human Papillomavirus; Participants will receive only the intervention strategies they need at strategic points. Timeline of the intervention delivery not drawn to scale.

2. INTRODUCTION

2.1 STUDY RATIONALE

The Cancer Prevention and Control Program within UCCC works to develop, evaluate, and disseminate evidence-based interventions for primary, secondary, and tertiary prevention, and to improve health services delivery for patients. Efforts to meet the Cancer Center's priorities include promoting awareness to increase vaccinations against HPV as part of its goal to eliminate HPV-related cancers in Colorado; giving priority to underserved Hispanic, residents in outlying rural areas, and residents living in areas of high poverty. This proposal leverages several ongoing community outreach efforts to improve HPV vaccine uptake, by educating and navigating patients where HPV vaccine rates are low and where HPV-related cancers are most prevalent.

2.2 BACKGROUND

[name] leads a supplemental award to the University of Colorado Cancer Center (UCCC; 3P30CA046934-31S4) by the National Cancer Institute (NCI) to enhance its community outreach and engagement to underserved populations (i.e., ethnic minority, low-income, uninsured, or underinsured) disproportionately affected by cancer incidence, mortality, and morbidity. More specifically, this project seeks to implement interventions to improve these

populations' knowledge, uptake, and completion of the human papilloma virus (HPV) vaccine to prevent HPV-related cancers. We will partner with Denver Health and Hospital Authority (DHHA) which serves communities with populations where HPV-related cancers' incidence, mortality, and burden are high. Denver Health mostly serves medically underserved patients with a significant percentage of patients covered by Medicaid (62%) and of patients without health insurance (14%). The Denver County population served by Denver Health is at high risk for cancer-related health inequities. The age-adjusted annual incidence of cervical cancer (cases per 100,000), using 2010-2014 county data,³⁵ is higher for Denver County (6.6) than for the state of Colorado (5.9). Cervical cancer and oropharyngeal cancers are the most common HPV-related cancers in women and men respectively, impacting more than 29,000 individuals in the US each year⁸. One model predicts that HPV infection can be eliminated with global 80% vaccination coverage, but even with more modest rates of vaccine uptake there can still be significant reductions in HPV-related malignancies. Statewide in Colorado in 2016 only 48% of adolescents had completed the HPV series¹³. Our intervention will focus on providing education delivered by Community Health Educators (CHEs) and on referring participants to Patient Navigators (PNs) who will facilitate their access to the HPV vaccine.

2.3 RISK/BENEFIT ASSESSMENT

2.3.1 KNOWN POTENTIAL RISKS

Loss of confidentiality for patients in the educational intervention delivered by the CHE.

2.3.2 KNOWN POTENTIAL BENEFITS

Improve knowledge about importance of HPV vaccine among parents of adolescents and young adults eligible for the vaccine and uptake of the vaccine among the interventions' participants.

2.3.3 ASSESSMENT OF POTENTIAL RISKS AND BENEFITS

This a minimal risk study that does not place participants in any increased risk of harm. Thus, the benefits to be gained in knowledge far out way the risks.

The risks to participants are reasonable in relation to the anticipated benefits to participants and/or society, and in relation to the importance of the knowledge that may reasonably be expected to result, thereby falling in favor of performing the study:

- To Participant: *Improved knowledge an intention to initiate or complete the HPV vaccine series.*
- To Society: *Increased uptake of the HPV vaccine, could lead to decreased rates of HPV related malignancies in a population that is disproportionately affected by HPV related malignancies.*
- Justify the importance of the knowledge gained: *We will gain understanding on how to implement a combination of a CHE and PN intervention to increase knowledge, intentions, and uptake of the HPV vaccine to prevent HPV-related malignancies in areas of most need. Additionally, we will evaluate the influence NCI designed educational presentations and materials on increasing*

knowledge and intentions about HPV and the HPV vaccine series. Exploring these interventions will shed knowledge on practices to use when addressing some of HPV-related cancers among underserved populations.

3 OBJECTIVES AND ENDPOINTS

OBJECTIVES	ENDPOINTS	JUSTIFICATION FOR ENDPOINTS
Primary	Parents & young adults' knowledge & intentions to obtain the HPV vaccine	Behavioral factors precede uptake of preventive vaccines
	Sociodemographic data (e.g., age, gender, ethnicity, insurance, income, zip code)	Variables known as associated with vaccine uptake
Secondary		
	Uptake of one, two, or three HPV vaccine doses among adolescents (9 to 17 years old) and young adults (18-26 years old).	Number of vaccine doses are used to assess full protection (3 doses) or partial (≤ 3 doses)
Tertiary/Exploratory	Intervention's delivery and patient-level & system-level impact.	Interventions that can be delivered to impact patients & clinics are easier to implement

4 STUDY DESIGN

4.1 OVERALL DESIGN

We will use a one-group post-test design to assess the effects of the intervention on the primary outcomes. The educational intervention will be delivered to 400 participants by a trained CHE who will deliver the educational materials to eligible DHHA patients. The CHE will administer the post-education survey at baseline to participants. Additionally, we will use a one-group post-test design to assess the impact of the intervention on the secondary outcomes. At the patient-level, we will track participants that receive (a) 1st dose, 2nd dose, or 3rd dose of the HPV vaccine; and the number of referrals to care by recording the number of patients received (b) referrals to health insurance, discount, or no-cost HPV vaccine programs; or (c) to other services to facilitate HPV vaccine dose completion. To assess clinic-level impact, we will track each clinic's HPV vaccine rates for adolescents (9-17 years old) and young adults (18-26) and compare rates from before we start the intervention and then quarterly thereafter we have introduced the intervention to each respective Denver Health clinic.

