4.2 SCIENTIFIC RATIONALE FOR STUDY DESIGN

This is a pragmatic study that seeks to evaluate in real-world practice the use of a CHE and PN intervention to improve the uptake of evidenced-based HPV vaccinations. Thus, it uses a post-design to evaluate participants' changes in knowledge and intentions to vaccinate by comparing

outcomes at baseline to outcomes after exposure to the CHE educational intervention. Similarly, it uses a post-test design to evaluate the uptake of the HPV vaccine after participating in the PN intervention. In real-world practice it is important to measure an intervention's impact not only at the patient-level but also at the clinic- and system-level. Consequently, we will measure post-intervention the rates of the HPV vaccine 1st dose, 2nd dose, and/or 3rd dose uptake for each clinic and for the DHHA systems by comparing its rates to state level HPV vaccine rates.

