7.3 LOST TO FOLLOW-UP

The evaluation of the educational intervention occurs at baseline during the post education survey. Our sample size of 200 will achieve 80% power the moment the 200th participant completes the post survey at baseline. Thus, lost to follow-up is not a concern in our study. Follow-up is only to capture vaccination status, as well as to facilitate patient navigation if it applies. Furthermore, follow-up will only occur for some participants. Only those that indicate at baseline not being vaccinated themselves or indicate being parents of children that have not been vaccinated will be contacted at 3 months post baseline. Similarly, only those that indicate not being vaccinated themselves or indicate having children not being vaccinated at 3 months post baseline will be contacted at 6 months post baseline. For those that are contacted at 3 months and 6 months, we will make a maximum of 6 contacts (e.g., phone calls, texts, or letters) to each consented participant. After 6 unsuccessful contact attempts, we will consider participant as “lost to follow up” and no longer make attempts to contact them.

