8.2.6 SCHEDULE OF EVENTS TABLE

HPV Educational Intervention and Data Collection	Baseline/ Intervention			Recall upon missed dose	Quarterly
Informed Consent	X				
Post-education (baseline survey)	X				
Gift card compensation	X				
PN vaccine referral/navigation	X			X	
PN vaccine follow-up/navigation				X	X
Clinic Assessment of HPV vaccination rates EMR system					X

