9 STATISTICAL CONSIDERATIONS

9.2 SAMPLE SIZE DETERMINATION

A sample size of 200 participants achieves 80.0% power to reject the null hypothesis of zero effect size (i.e., improvement in, HPV and HPV vaccine knowledge, and HPV vaccine intentions' scores) when the Cohen's effect size is 0.20 (small effect size)³⁴ and the significance level is 0.050 using a two-sided one sample paired t-test.

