9.4 STATISTICAL ANALYSES

9.4.1 GENERAL APPROACH

The effects of the education intervention on the primary outcomes measured by the continuous scales regarding, HPV and HPV vaccine knowledge, and HPV vaccine intentions, will be assessed using two-sided one-sample paired t-test for the null hypothesis that the paired difference is 0 against the alternative hypothesis that the paired difference is not 0. Appropriate transformation and/or the non-parametric Wilcoxon test will be performed if the data suggests severe non-normality. The significant level is 0.05.

Exploratory analysis of the characteristics that influence participants' adherence (0=non-adherent; 1=adherent) to the recommended HPV vaccine dosage will be conducted use logistic regression analysis. Our analyses will adjust for co-variates that likely influence the primary outcomes and exploratory outcomes, which include prior HPV vaccine dosage. We will also adjust for other potential co-variates if our descriptive analysis suggests this may be needed. Summary descriptive statistics will be calculated and presented for all primary, exploratory outcomes for all participants, and for subgroups defined by participants predisposing (e.g., gender, age), enabling (e.g., insurance, barriers), and need (e.g., cancer risks) characteristics. The demographic characteristics of the participants will be presented with descriptive statistics also. The means, medians and the 95% confidence intervals will be calculated for continuous variables; the frequencies, estimated rates, and the exact 95% confidence intervals will be calculated for the binary and categorical variables.

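### The primary analysis is a paired before/after test, but the protocol schedules only one knowledge and intentions survey, given after the education

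*Protocol*

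**What the plan says.** The first primary endpoint in section 1.1 is "Knowledge and intentions to initiate or complete the HPV vaccine series among project participants", and the matching objective is to improve both.

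**Passages that need two scores per person**
- Section 4.2 promises to evaluate changes by comparing "outcomes at baseline to outcomes after exposure to the CHE educational intervention".
- Section 9.2 sizes the study for improvement in the scores: 200 participants, Cohen's effect size 0.20, 80.0% power, where "the significance level is 0.050 using a two-sided one sample paired t-test".
- Section 9.4.1 says the primary outcomes "will be assessed using two-sided one-sample paired t-test for the null hypothesis that the paired difference is 0", with a transformation or a Wilcoxon test if the data are severely non-normal.

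**Passages that provide one score per person**
- Section 4.1: "We will use a one-group post-test design to assess the effects of the intervention on the primary outcomes". It adds that the post-education survey is given at baseline.
- Section 7.3: "The evaluation of the educational intervention occurs at baseline during the post education survey". It restricts follow-up to vaccination status and navigation, and only for some participants.
- Section 8.1 names an immediate post-education survey and no earlier one.
- Section 8.2.6 has a single survey row, labelled "Post-education (baseline survey)", marked once.

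**The concern.** A paired test needs a score before and a score after the education from the same person. Here the survey called baseline is itself the post-education survey, so the comparison promised in section 4.2 has nothing on its *before* side.

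The primary hypothesis of zero paired difference would then be untestable. A single post-education score in one group cannot separate what the session taught from what participants already knew or intended. The protocol gives no external reference value for these scales that could serve as a no-effect benchmark. Section 7.3 also relies on the power claim when it says loss to follow-up is not a concern, so that argument falls with it.

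The matter is urgent because a pre-education score cannot be collected once a participant has had the session. A statistical analysis plan could not repair this, since it cannot create a measurement that the schedule does not collect.

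**Working it through.** **1. Reproduce the stated power.** Inputs from section 9.2: n = 200, effect size d = 0.20 (read as mean paired difference divided by the SD of the paired differences), two-sided alpha 0.05, paired t-test.

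- Exact power uses the noncentral t distribution with n − 1 = 199 degrees of freedom and noncentrality d × √n = 0.20 × √200 = 2.83. Result: **80.4%**.
- The smallest n with at least 80% power is **199**.
- Normal approximation: n = ((1.960 + 0.842) / 0.20)² = 196.2, rounded up to **197**.

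The stated 80.0% at 200 participants is therefore right for a paired design.

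**2. Count the measurement occasions for knowledge and intentions.**

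| Section | Before education | After education |
|---|---|---|
| 4.1 Overall Design | none | one |
| 7.3 Lost to Follow-up | none | one; later contacts are for vaccination status and navigation |
| 8.1 Study Procedures | none | one, immediately after |
| 8.2.6 Schedule of Events | no row | one row, marked once |
| Needed by 4.2, 9.2 and 9.4.1 | one | one |

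Paired differences available as specified: **0 of 400**. Power for the paired test is undefined, because the test statistic cannot be formed.

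**3. Look for a second score elsewhere.**
- Section 8.1 mentions a 3-month follow-up survey. It goes only to some participants, section 7.3 limits its purpose, and any score it gave would be a second post-education score.
- The Wilcoxon alternative in section 9.4.1, as a substitute for the paired t-test, needs the same pairs.
- Section 4.1 does compare clinic vaccination rates before and after the start of the intervention, but these are not the knowledge and intention scores.

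**4. What post-only data can deliver.** The 95% CI half-width for a mean score, in SD units, is about 1.96 / √n:
- n = 200: 1.96 / 14.14 = **0.139 SD**
- n = 400: 1.96 / 20 = **0.098 SD**

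**5. What a pre-education survey would deliver.** With d = 0.20 and two-sided alpha 0.05, power is 80.4% at n = 200 and 97.9% at n = 400. The stated sample size would not need to change.

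**The case against.** The best counter-argument is that the instrument is not shown. Section 1.1 refers to pages 1-3 of an NCI survey, and a single post-session form could ask people to recall what they knew or intended beforehand. That would give a pair and would fit the wording of section 4.2. It cannot be ruled out, and the delivery schema figure is also not visible. But no readable passage mentions retrospective items, and the schedule table, which is readable, has one survey row. If such items exist, sections 4.2 and 9.4.1 would have to name them as the source of the pair, so the text needs correcting either way.

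A second argument is that post-test only is the deliberate, pragmatic choice, and that the analysis sections are what should change. That is a legitimate way to resolve the contradiction. Section 9.4.1 already plans means, medians and 95% confidence intervals, and the second primary endpoint, on sociodemographic associations, does not require a pre-test. What fails is the claim to show improvement.

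Third, a one-group before/after comparison has no control either. This stands: a measured change would not by itself separate the education from test-retest effects. It would, however, make the stated primary test computable.

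**Conclusion.** The concern holds. The protocol's primary test and power statement belong to a pre-test/post-test design, while the design, procedures and schedule describe a single post-education measurement. As specified, there are 0 paired differences among 400 participants. The first primary objective, improved knowledge and intentions, cannot be answered, and the 80% power does not apply to the design as written. The fault is the mismatch between design and analysis and not the power calculation.

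This rests on two readings: that the survey contains no retrospective pre-session items, since none are mentioned, and that the missing figures do not show a pre-education survey that the text and the schedule table omit. The contradiction must be resolved before the primary analysis can be carried out.

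**What to change.** **Preferred, if improvement is to be claimed.** Amend sections 4.1 and 4.2 to a one-group pre-test/post-test design. Give the same knowledge and intention items once after consent and immediately before the education, and again directly after it. Add a pre-education survey row to section 8.2.6, and use the word baseline only for that survey, in sections 1.1, 4.1, 5.5, 7.3 and 8.2.6. Sections 10.1.1.1 and 10.1.1.2 already place consent before any educational material, so the survey can fit the same contact. Where materials are sent by REDCap link (section 8.1), the pre-education survey should have to be completed before they open. If retrospective items are what was intended, name them and define the pair in section 9.4.1.

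The cost is a protocol amendment and, as an assumption, a few extra minutes per participant without extra visits. The suitability of survey pages 1-3 for use before the session has to be checked. The pre-test may sensitise participants, and the lack of a control group should be stated as a limitation.

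**Otherwise, and for anyone already surveyed only after the education.** Remove the paired t-test and its Wilcoxon alternative from section 9.4.1, the power claim from sections 9.2 and 7.3, and the language of improvement and change from sections 1.1, 4.2 and 9.2. Report post-education scores descriptively with 95% confidence intervals. This costs only wording.

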We will track HPV vaccine doses at the patient-level and rates at DHHA clinics to the access the system-level impact of the interventions on increases overall HPV vaccination rates for adolescents (9-17 years old) and young adults (18-26) in the respective DHHA clinics. Our goal is to conduct the educational sessions and the post education survey in person. However, current circumstances as a result of the COVID-19 outbreak require we execute our educational sessions remotely. We will send educational material to be watched via REDCap links or present the materials over Zoom or over the phone. Secured REDCap links will be used to obtain the post education survey. We will also use REDCap to obtain any PHI needed to for follow up.

Post education surveys will be physically mailed, without any PHI, to the NCI after we have uploaded and stored the surveys in REDCap.

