10.1.1.2 CONSENT PROCEDURES AND DOCUMENTATION

Informed consent process will be initiated prior to the individual's agreeing to participate in the study and continues throughout the individual's study participation. Extensive discussion of risks and possible benefits of participation will be provided to the participants and their families.

Consent forms will be IRB-approved, and the participant will be asked to read and review the document. The consent process will occur over the phone. All participants will receive a verbal explanation in terms suited to their comprehension of the purposes, procedures, and potential risks of the study and of their rights as research participants. Consent will be reviewed prior to participants receiving in any of the educational materials and before completing the surveys. The consent form will be read, and clarification will be confirmed, and questions will be addressed as needed. Participants will have time to review the consent prior to deciding if they would like to participate and will verbally acknowledge understanding and willingness to participate in the study prior to any procedure being done specifically for the study. We are unable to hold in person meetings due to COVID-19 restrictions. At this point in time those restrictions will remain indefinitely. Hosting virtual education sessions requires a high level of computer and technological literacy that has become a barrier to enrollment. Similarly, asking patients to complete a consent form that requires a digital e-signature and join a zoom call is too cumbersome and creates a barrier to enrollment. Thus, we will use a postcard consent that will be sent via text or email or will otherwise be made available to the subject in advance of the informed consent discussion. The participants may withdraw consent at any time throughout the course of the trial. The rights and welfare of the participants will be protected by emphasizing to them that the quality of their medical care will not be adversely affected if they decline to participate in this study.

The study allows the inclusion of non-English speaking and non-reading participants. Witnesses to these consent processes will be individuals not associated with the trial and will not have a conflict of interest.

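### The clinic-level before/after comparison cannot separate background or seasonal change from an intervention effect, and the error could run in either direction

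*Protocol*

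**What the plan says.** Protocol section 4.1 sets the clinic-level contrast: for adolescents and young adults separately, the investigators will "compare rates from before we start the intervention and then quarterly thereafter we have introduced the intervention to each respective Denver Health clinic". The tertiary/exploratory list in the Synopsis (section 1.1, item 3) has the same structure, with dose counts at baseline and then each quarter, taken from records the study will already hold: "To assess clinic-level impact, we will obtain clinic vaccination reports".

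Section 4.2 adds an external reference. Post-intervention uptake will be assessed "for each clinic and for the DHHA systems by comparing its rates to state level HPV vaccine rates".

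On timing, the Synopsis gives "Study Duration: 36 months". Section 8.1 says that "current circumstances as a result of the COVID-19 outbreak require we execute our educational sessions remotely", and section 10.1.1.2 says of the limits on in-person contact: "At this point in time those restrictions will remain indefinitely". No section dates the clinic baseline or gives a clinic's size or vaccination rate.

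On rank, secondary objective 2 in section 1.1 includes assessing the effect of navigation at clinic and system level. The matching endpoint is tertiary/exploratory, both in the Synopsis and in the section 3 table.

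**The concern.** A single before period set against later quarters attributes every change over time to the intervention. Three other sources of change are plausible here: a trend already under way, the season (a before quarter and an after quarter may fall at different times of year), and changes in clinic attendance while COVID-19 restrictions applied, tightened or eased. As stated, the contrast has no element that separates these from the intervention.

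What is at stake is the clinic- and system-level conclusion that secondary objective 2 calls for. If background rates rise, an ineffective programme could look effective. If they fall, an effective one could look useless. Knowledge, intentions and dose uptake among participants do not depend on this comparison.

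**Working it through.** **The plan's own figure.** The protocol gives no power or precision figure for clinic rates. Its only power statement (section 9.2) concerns participant scores: 200 participants, effect size 0.20, two-sided 0.05, 80.0% power. The noncentral t distribution gives 80.4%, so that figure reproduces, but it does not bear on this point.

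**Step 1: what each comparison removes.**
- Section 4.1, clinic before against clinic after: removes fixed differences between clinics, but no change over time.
- Section 4.2, clinic or system after against state after: shares the calendar period, but compares levels. Section 2.2 describes the patients as 62% Medicaid and 14% uninsured, so a gap from the state may reflect who the patients are.
- A difference in changes (clinic after minus before, less state after minus before, in the same quarters) would remove both fixed differences and shared drift. Neither section states it.

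**Step 2: largest possible intervention effect on a clinic's rate.** Inputs from the protocol: "Minimum number of participants to be enrolled 400"; a cap of 1000 (section 1.1); 12 clinics listed in section 5.1. Assumptions: participants spread evenly, one eligible patient per participant, every participant gaining a dose because of the study, a rate defined as coverage of all eligible patients, and 500 to 5,000 eligible patients per clinic.

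Participants per clinic: 400/12 = 33.3; 1000/12 = 83.3. Maximum rise in points = 100 × participants per clinic / eligible patients.

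| Eligible patients per clinic | 400 participants | 1000 participants |
|---|---|---|
| 500 | 6.7 | 16.7 |
| 1,000 | 3.3 | 8.3 |
| 2,000 | 1.7 | 4.2 |
| 5,000 | 0.7 | 1.7 |

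Drift equals this ceiling when eligible patients = participants per clinic / drift. For an assumed 2-point drift that is 33.3/0.02 ≈ 1,667 patients (400 participants) or 83.3/0.02 ≈ 4,167 (1000 participants). For 5 points it is about 667 or 1,667. Above these sizes the drift exceeds the largest possible effect.

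**Step 3: how often drift alone would look like an increase.** This is an illustration only, since section 9.4.1 plans no clinic-level test. Take zero intervention effect, an after rate of 48% (the 2016 state completion figure in section 2.2, used only as a level), a before rate lower by the drift s, N patients in each period treated as independent, and a two-sided 0.05 z-test.

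P(significant increase) = Φ((s − 1.96·SE₀)/SE₁), where SE₀ uses the pooled rate and SE₁ the separate rates. For N = 1,000 and s = 0.02: SE₀ = √(2 × 0.47 × 0.53/1000) = 0.0223; SE₁ = √((0.46 × 0.54 + 0.48 × 0.52)/1000) = 0.0223; (0.02 − 0.0437)/0.0223 = −1.06; probability 14%.

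| N per clinic | 2-point rise | 5-point rise |
|---|---|---|
| 500 | 9% | 35% |
| 1,000 | 14% | 61% |
| 2,000 | 24% | 89% |
| 5,000 | 52% | 99.9% |

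The nominal chance of a false increase is 2.5%. Pooling 12 clinics of 1,000, a 2-point rise gives 87%. A background fall works in mirror image and would hide a real gain.

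**The case against.** - **There is a comparator.** Section 4.2 brings in state rates, which share the calendar period. This stands in part: it is wrong to call the plan a before/after comparison and nothing more. But a comparison of post-intervention levels does not remove drift, and nothing says the state figures will match the clinic quarters.
- **The direction of bias is unknown.** A reader might infer that the before period sits in a pandemic trough, so that recovery would be credited to the programme. The documents do not support this. They show that sessions and consent became remote, but say nothing about vaccination rates and do not date the baseline. A pre-pandemic baseline could push the bias downward. This objection stands.
- **The endpoint is exploratory, and no clinic-level test is planned.** Both are true, and they limit the weight of the point. Section 9.4.1 offers descriptive rates with intervals and no clinic-level model. Even so, sections 1.1, 4.1 and 8.1 speak of impact, which is a causal reading.
- **Trend and season terms may be in an SAP that is not shown.** The modelling detail may be. The choice of contrast and the absence of control clinics are set in section 4.1.
- **Staggered starts.** A reader might infer from section 4.1 that clinics begin at different times and so provide free concurrent controls. The wording only hints at this, and no rollout schedule is given.
- **The arithmetic shows dilution, and a better model may still miss a small effect.** This is fair. It also depends on clinic sizes the protocol does not give and on what the rate means: the Synopsis counts patients receiving doses, while section 4.1 speaks of rates. A sounder model makes the estimate interpretable without making it precise.

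**Conclusion.** The point holds as a limitation of interpretation on a tertiary/exploratory endpoint that serves secondary objective 2. As written, sections 4.1 and 4.2 do not separate the intervention from background or seasonal change, and the resulting error could be in either direction.

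Its size cannot be fixed from the documents. Under the assumptions in the working, the ceiling on a true effect runs from 6.7 down to 0.7 points at 400 participants and from 16.7 down to 1.7 at 1000, so drift of a few points could match or exceed it in larger clinics. In a clinic of 500 at the enrolment cap it would not. The drift figures are assumed, not observed. It would go too far to say that an ineffective programme would appear to work, or that drift would swamp any effect. Primary and secondary participant-level results are untouched.

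**What to change.** In section 4.1, state that several pre-intervention quarters per clinic will be extracted from the same clinic reports. Eight is a reasonable example, since it gives each calendar quarter twice before the start. Analyse them with an interrupted time series that includes calendar-quarter terms and each clinic's own start quarter, and state the dates of the baseline and whether the rate is coverage or doses given per quarter.

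A series within one clinic cannot by itself remove a shock that coincides with the start. Where same-quarter state rates are available, therefore, compare them as a difference in changes rather than as post-intervention levels. Use clinics that have not yet started as comparators only if starts are in fact staggered.

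If this is not done, report the clinic rates as descriptive and make no claim of intervention impact.

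The cost is one retrospective data extraction and a modest model. Estimates will be less precise and possibly less favourable. The descriptive alternative costs a sentence, plus giving up the clinic-level causal claim.
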